### 4.2 Analysis principles

Unless otherwise specified, all tests will be two-sided and p-values of less than 0.05 will be considered as evidence of a difference between treatment arms.

Multiple comparisons will be performed and this may increase the probability of observing a statistically significant result by chance. No adjustments will be made to account for multiple testing.

P-values will be reported to four decimal places with p-values less than 0.00005 as <0.0001. SAS or R will be used to conduct analyses.

All analyses will be adjusted for the stratification variable (recruitment site). Recruitment site will be accounted for by including a random effect in each model.

All hazard, odds and rate ratios will be presented as active treatment versus placebo. A ratio which is greater than 1 indicates that the hazard, odds or rate is greater in the active treatment arm. 95% confidence intervals will be presented with all ratios. P-values for regression models will be obtained by comparing  $-2 \times \log\text{-likelihood}$  values for models with and without the treatment term.

The key demographics and clinical condition of the participants at consent will be presented for each arm of the trial to describe the cohort. A CONSORT diagram will be presented to show how participants progressed through the trial.

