There is a lack of a relationship between platelet count and bleeding risk, except at very low platelet counts. PLADO reported that patients had similar rates of bleeding (17%) with morning platelet counts within the wide range of 6 to 80 x 10⁹/L ([16](#)).

The burden of bleeding varies in sub-groups of patients, e.g. higher bleeding rates in patients with acute leukaemia or receiving an allogeneic stem cell transplant (SCT), lower rates in patients receiving an autologous SCT([21](#)).

Taken together, these findings suggest that current policies for prophylactic platelet transfusions have a limited role in reducing much of the bleeding seen in haematology patients undergoing intensive chemotherapy and/or stem cell transplantation. There is a need for new treatment strategies to minimise the burden of bleeding, particularly in high risk groups of patients.

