#### 1.5.2 Primary efficacy outcomes

616 participants will be accrued to the UK/Australian clinical trial.

The participants will be randomised in a double blind fashion to receive TXA or a matching placebo.

The clinical trial will be conducted with the primary endpoint of decreased proportion of death or WHO Grade 2 or higher bleeding among all participants receiving TXA versus placebo over 30 days. The type 1 error will be controlled at a two-sided level of 0.05. The primary endpoint will be analysed using the Kaplan-Meier (KM) method to estimate the probability of bleeding or death within 30 days in the analysis populations. Power and sample size calculations are based on a log-rank test for comparing two survival curves, as described in Collett.

It is anticipated that the UK and Australia will be able to recruit 616 participants for this trial. Under the assumption that anti-fibrinolysis results in a decrease of death or WHO Grade 2 bleeding from 43% to 32%, the 616 participants will provide 80% power to detect an observed absolute decrease in bleeding rates of 11% (a relative reduction of 26% with a NNT of 8.9) and will be judged statistically significant at the two-sided 0.05 level. The planned trial size of 616 subjects includes an additional 5% of participants above the required sample size of 586. This 5% figure is more than the proportion of participants within TOPPS (4%) that dropped their platelet count below  $50 \times 10^9/L$  but did not drop their platelet below  $30 \times 10^9/L$ . This therefore accounts for the number of participants within the trial who are randomised but never receive the trial treatment.

We do not expect there to be a problem with the assessment of the primary outcome of bleeding over the 30 day trial period, starting from the first day of administration of the study intervention. In the recent TOPPS trial, completeness of bleeding outcome documentation was

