## Statistical Analysis Plan

---

for safety analyses of thrombotic events will be all participants who receive any amount of trial treatment, using data gathered from time of consent until 120 days after first administration of trial treatment.

In addition, a multivariate test for heterogeneity of UK and Australian baseline participant characteristics will be performed by the trial statistician. The population used for this analysis will be a modified intention to treat population including all eligible randomised participants whose platelet count falls to  $30 \times 10^9/L$  or below. Sex, diagnosis (acute leukaemia or not) and treatment plan (autograft or not) will be analysed as binary outcomes. The normal approximation to the binomial will be applied for each binary variable and sex, diagnosis (acute leukaemia or not), treatment plan (autograft or not) and haemoglobin at randomisation will be compared using Hotelling's T-squared test, as long as the following criteria are fulfilled: (i) the estimated proportions are not close to the [0, 1] boundaries; (ii) the number of participants in each binary outcome category is  $> 5$ ; (iii) for each binary variable, 3 standard deviations above and below the expected proportion is within the range [0, 1]. If not all the criteria are fulfilled, an alternative test will be considered: a logistic regression of participant country (UK or not) on sex, diagnosis (acute leukaemia or not), treatment plan (autograft or not) and haemoglobin at randomisation will be performed and the concordance statistic and its 95% confidence interval will be calculated. A confidence interval that does not include 0.5 would indicate evidence of a difference between UK and Australian participants. A summary of the multivariate test will be provided to the Data Monitoring Committee. Only strong evidence of a difference between UK and Australian participants will be considered as evidence of heterogeneity. If evidence of heterogeneity between UK and Australian participants is identified in the interim analysis, subgroup analysis by country of participant will be performed for the primary outcome in the main analysis.

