### 4.6 Sub-Group analyses

Subgroup analyses will be performed for the primary outcome in the main analysis by including an interaction term. Analysis will be performed using the same methods as for the primary outcome, except a covariate and treatment-covariate interaction will be included in the model for each of the following variables in turn:

- Country of participant (UK vs. Australia), if evidence of heterogeneity between UK and Australian participants is identified in the interim analysis
- Platelet count at consent ( $\leq 30 \times 10^9/L$  vs.  $> 30 \times 10^9/L$ )

Treatment compliance during first 30 days of the trial (participant decided to stop taking trial treatment vs. participant did not decide to stop taking trial treatment). Although participants may decide to stop taking trial treatment for many reasons, the main reason is thought to be an unwillingness to take the large, over-encapsulated oral trial treatment. The over-encapsulated oral trial treatment is to be replaced with smaller tablets in the UK and Australia. Therefore, an additional analysis of treatment compliance will be performed using four mutually-exclusive categories: participant decided to stop taking trial treatment during the period of over-encapsulated oral treatment; participant decided to stop taking trial treatment during the period of oral treatment as tablets; participant did not decide to stop taking trial treatment during the period of over-encapsulated oral treatment; participant did not decide to stop taking trial treatment during the period of oral treatment as tablets. The number of UK participants who discontinued IV trial treatment during the period in September 2018 when oral treatment was unavailable will be described by arm.

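### The primary Cox model adjusts for site only and leaves out diagnosis and treatment plan, which the protocol itself calls prognostic; the analysis is valid but gives up roughly 1 to 8 points of power

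*SAP*

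**What the plan says.** SAP 4.2 sets the rule for every model: "All analyses will be adjusted for the stratification variable (recruitment site", with site entered as a random effect. Protocol 11.5.1 says the same, and the footnote to the primary outcome table in SAP 5.4 lists centre as the only adjustment. Randomisation is stratified by site alone (protocol 5.4 and 11.1, SAP 1.4).

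Protocol 1.2 describes the case mix differently: "The burden of bleeding varies in sub-groups of patients, e.g. higher bleeding rates in patients with acute leukaemia" or allogeneic transplant, with lower rates after autologous transplant. It draws the conclusion: "There is a need for new treatment strategies to minimise the burden of bleeding, particularly in high risk groups of patients".

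Both variables are available. Form 3, diagnosis and treatment plan, is mandatory at consent (SAP 3.1), and both are tabulated by arm (SAP 5.3). Their only analytic use is the interim comparison of the UK with Australia in SAP 4.1: "Sex, diagnosis (acute leukaemia or not) and treatment plan (autograft or not) will be analysed as binary outcomes".

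For subgroups, SAP 4.6 says that "a covariate and treatment-covariate interaction will be included in the model for each of the following variables in turn". The variables are country (only if the interim test shows heterogeneity), platelet count at consent, and treatment compliance. None is diagnosis or treatment plan. The sensitivity analyses in SAP 4.7 do not use them either.

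**The concern.** The trial pools leukaemia chemotherapy, allograft and autograft, which the protocol says bleed at different rates. In a Cox model, omitting a strong baseline predictor pulls the treatment hazard ratio towards 1 relative to the hazard ratio within risk groups, and costs power. The factors here are named in the protocol, recorded for everyone before randomisation, and already coded as binary for another purpose. The sample size has little slack (about 80% power at the 586 required), so a few points gained without extra participants are worth having. Covariates added after unblinding would carry little weight, so the choice has to be made beforehand.

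**Working it through.** **Inputs from the documents (SAP 1.5.2, protocol 11.3.2).** On alpha: "The type 1 error will be controlled at a two-sided level of 0.05". On event risks at 30 days: a "decrease of death or WHO Grade 2 bleeding from 43% to 32" per cent. Power 80%, log-rank test, 586 required, 616 after adding 5%.

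**Step 1: reproduce the sample size.**
- HR = ln(0.68)/ln(0.57) = 0.686, so ln HR = -0.3768.
- Events (Schoenfeld) = 4 × (1.960 + 0.8416)² / 0.3768² = 221.2.
- N = 221.2 / 0.375 = 590, within 1% of 586; 586 × 1.05 = 615.3, hence 616.
- Power at 586: events = 586 × 0.375 = 219.75, and Φ(0.3768 × √219.75 / 2 - 1.960) = 79.7%. At 616 it is 81.7%.

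The planned figure is not in dispute.

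**Step 2: assumptions the documents do not supply.** Two risk groups, autograft (35-40% of participants) and other, with placebo risks averaging 43%. A common within-group hazard ratio h is chosen so that the overall TXA risk is 32%. In the widest case (share 0.40, risks 15% and 61.7%), h solves 0.40 × (1 - 0.85^h) + 0.60 × (1 - 0.383^h) = 0.32. This gives h = 0.654 and TXA risks of about 10.1% and 46.6%.

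**Step 3: power.** 3,000 simulated trials of 586 per row, exponential times, Cox model without and with the group as covariate, site effect left out. The Monte Carlo standard error of each power is about √(0.8 × 0.2 / 3000) = 0.7 points.

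| Autograft share | Placebo risk, autograft v other | Within-group HR | Unadjusted | Adjusted |
|---|---|---|---|---|
| 40% | 33% v 50% | 0.682 | 79.8% | 80.3% |
| 35% | 25% v 53% | 0.676 | 79.3% | 81.9% |
| 40% | 20% v 58% | 0.665 | 80.2% | 84.6% |
| 40% | 15% v 62% | 0.654 | 80.7% | 88.0% |

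Allowing for simulation error, that is about 78-81% unadjusted and 80-88% adjusted.

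Three groups (30% autograft, 45% other chemotherapy, 25% high risk), with the same overall risks, agree. Placebo risks of 31/46/52% give 80.9% and 81.6%; 22/47/61% give 80.3% and 84.5%; 14/46/71% give 80.6% and 87.3%. With no prognostic effect the figures are 78.3% and 78.4%.

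**Step 4: where the gain comes from.** The standard error of the log hazard ratio hardly moves (0.137 in both models). The gain comes from the adjusted hazard ratio lying further from 1. Variance does fall for the risk difference: compare the sum over arms of p(1 - p) with the sum over arms of the within-group average of p(1 - p). In the widest case these are 0.2451 + 0.2176 = 0.4627 and 0.1928 + 0.1856 = 0.3784, a ratio of 0.82. In the three-group cases the fall is 2-16%. This benefit reaches the reported risk difference and NNT only if they too are computed with the covariates.

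**Step 5: an interaction test.** With 219.75 events split between two subgroups, SE = √(4/d₁ + 4/d₂). A 50:50 split gives 0.270 and power Φ(0.3768/0.270 - 1.960) = 29% to separate HR 0.686 from 1.0. A 30:70 split gives 0.294 and 25%. For 80% power the ratio of hazard ratios would have to be about 0.44 to 0.47.

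**The case against.** Adjusting for the stratification factor alone is a defensible choice. It raises no problem of bias or type I error. Chance imbalance in case mix is already covered by the confidence interval, and the plan tabulates both factors by arm. A random site effect may absorb some case mix, so the real gain could be smaller than in the table. Every group rate is assumed, and under the mildest spread the gain is within simulation error. All of that stands; it limits the size of the point but not its direction.

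Two stronger readings are tempting, and the documents support neither.

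- A reader might infer that the planned analysis is underpowered, at 70-78%. That figure appears if the design hazard ratio of 0.686 is placed inside each risk group. Doing so shrinks the overall effect: with placebo risks of 25% v 53%, 20% v 58% and 15% v 62%, the overall differences become 10.6, 10.2 and 9.9 points, and Schoenfeld power for those is 77%, 74% and 70%. The plan specifies 43% v 32% overall, and at that effect the unadjusted analysis keeps its 80%.
- A reader might infer that the trial fails to answer one of its own questions, whether TXA works in high-risk groups. That sentence belongs to the background. The stated aim (SAP 1.1, protocol 1.7) concerns the whole population. An autograft-v-other contrast would also pool the named high-risk groups with everyone else, and it has only 25-29% power.

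**Conclusion.** The point holds as one of efficiency. The planned primary analysis is valid and meets its power target, but it passes over two baseline factors that the protocol identifies as prognostic and collects for every participant. The likely gain is about 1 to 8 points of power, from about 78-81% to about 80-88%. This assumes autograft-v-other placebo risks between 33% v 50% and 15% v 62%, an autograft share of 35-40%, a common within-group hazard ratio, overall risks of 43% v 32%, and 586 analysed. If the factors are not prognostic, power is essentially unchanged. The change is worth making because it costs little, not because the present analysis is wrong.

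**What to change.** Before unblinding:

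1. In SAP 4.2/4.3 and protocol 11.5.1, add diagnosis (acute leukaemia or not) and treatment plan (chemotherapy, autograft, allograft, other) as fixed covariates in the primary Cox model, keeping the random site effect. The level for other plans is needed because SAP 5.3 lists them.
2. State that missing diagnosis or treatment plan gets its own category. SAP 4.8 excludes missing baseline data from the relevant analyses and the table in SAP 5.1 allows for both to be missing, so without this rule mITT participants could drop out of the primary analysis.
3. Keep the site-only model as a named sensitivity analysis in SAP 4.7, and change the footnote in SAP 5.4. Say whether the risk difference and NNT stay unadjusted for these factors or are standardised over them.
4. Optionally, add a treatment-by-treatment-plan or treatment-by-diagnosis interaction in SAP 4.6 and protocol 11.5.3, labelled exploratory and reported as hazard ratios with confidence intervals.

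The cost is wording in both documents and no new data. The few extra coefficients are modest against about 220 expected events. The small downside is that the hazard ratio becomes conditional on these factors, and the optional step adds one more unadjusted test.

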## Statistical Analysis Plan

---

### 4.2.1 Efficacy population

The population used for efficacy analyses will be a modified intention to treat population (mITT) including all randomised participants whose platelet count falls to  $30 \times 10^9/L$  or below. Data are gathered for 30 days from the day the first dose of trial treatment is administered or is planned to be administered for those participants who did not receive treatment. Participants will be analysed in the arm that they were randomised to. Randomised participants whose platelet counts do not fall to  $30 \times 10^9/L$  or below will be excluded from the analysis, as will participants who develop exclusion criteria after randomisation and prior to their count falling to  $30 \times 10^9/L$  or below. These exclusions are deemed appropriate as the early randomisation is for pragmatic reasons only. Characteristics of all randomised participants will be compared to the mITT population to ensure that excluded participants are similar across the arms.

Unless otherwise specified, all analyses will be by this mITT. All subjects who fulfil the mITT requirements will be included in the analyses. Subjects whose platelet count falls to  $30 \times 10^9/L$  or below will be included in the analyses, even if they were randomised in error, did not receive trial treatment, stopped trial treatment "early", or received prophylactic transfusions not in accordance with the protocol.

**Rationale:** Owing to the emergent nature of treatment of thrombocytopenic participants, participants are randomised in a double blind fashion to the treatment arms when platelet levels drop below  $50 \times 10^9/L$ . This will allow time for the pharmacy to prepare the trial treatment, and for the trial treatment to be available when the platelet count falls to  $30 \times 10^9/L$  or below. This has been instituted for pragmatic reasons and will guard against delays in the availability of the trial treatment.

The main outcome analysis will be based on the mITT population. However, a per-protocol analysis of the primary outcome will also be performed. This per-protocol analysis will exclude all participants who were randomised in error and all participants who did not adhere to a set of minimum protocol-adherence criteria during the first 30 days of the trial. The criteria are:

- The participant commenced trial treatment within 72 hours of the first recorded platelet count  $\leq 30 \times 10^9/L$ , OR if the participant was admitted with a platelet count already below  $30 \times 10^9/L$  within 72 hours after the start of chemotherapy or conditioning for a stem cell transplant.
- The participant received trial treatment and only received the trial treatment prescribed to them and did not receive open label tranexamic acid, other antifibrinolytic agent or procoagulant drug
- The participant only received the correct dose of the trial treatment prescribed to them.
- The participant did not receive trial treatment after the point at which discontinuation of trial treatment should have occurred.

Participants who did not meet all the trial eligibility criteria and/or met at least one of the trial exclusion criteria will be considered as randomised in error. Participants who were randomised in error and received study intervention will be considered a protocol deviation. Participants who withdrew from the trial after starting trial treatment, who missed a dose of trial treatment or who chose to stop trial treatment "early" are included in the per protocol analysis.

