The main primary outcome analysis will be based on the mITT population. However, a per-protocol analysis of the primary outcome will also be performed. This per-protocol analysis will exclude all participants who were randomised in error and all participants who did not adhere to a set of minimum compliance criteria during the first 30 days of the trial. The criteria are:

- The participant commenced trial treatment within 72 hours of the first recorded platelet count $\leq 30 \times 10^9/L$, OR if the participant was admitted with a platelet count already below $30 \times 10^9/L$ within 72 hours after the start of chemotherapy or conditioning for a stem cell transplant.
- The participant received trial treatment and only received the trial treatment prescribed to them and did not receive open label tranexamic acid, other antifibrinolytic agent or procoagulant drug
- The participant only received the correct dose of the trial treatment prescribed to them
- The participant did not receive trial treatment after the point at which discontinuation of trial treatment should have occurred

Participants who did not meet all the eligibility criteria and/or met at least one of the exclusion criteria will be considered as randomised in error.

- **Safety population (apart from thrombotic events)**

The population used for safety analyses will be all participants who receive any amount of trial treatment, using data gathered from first administration of trial treatment until up to 120 days after first administration of trial treatment.

- **Thrombotic Event Safety population**

The population used for safety analyses of thrombotic events will be all participants who receive any amount of trial treatment, using data gathered from time of randomisation until 120 days after first administration of trial treatment.

- **Stopping rules**

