20.2. WHO Grading System

General Definitions of WHO Grades

Grade 4

Any bleeding that is:

- Fatal
- Life-threatening. For example:
 - Bleeding that requires transfer to intensive care/treatment unit
 - Bleeding that is associated with haemodynamic instability and causes inadequate tissue perfusion
- Evidence of inadequate tissue perfusion could include:
 - Hypotension
 - Systolic blood pressure (BP) < 90mmHg
 - >40mmHg fall in systolic BP
 - Mean arterial pressure (MAP) <65mmHg
- In absence of hypotension, markers of inadequate tissue perfusion include increased blood lactate, increased base deficit, perfusion-related low pH (if other causes of metabolic acidosis (e.g. sepsis) are not present)

(Please also see organ-specific definitions)

Grade 3

Any bleeding that does not fulfil the criteria for grade 4 bleeding (general or organ-specific) BUT requires:

- Red cell transfusion specifically related to treatment of bleeding within 24 hours of onset of bleeding, for example:
 - Required to treat fall in haemoglobin of at least 2g/dl within preceding 24 hours without evidence of haemolysis
 - No haemoglobin increment within 24 hours of at least a 2 unit red cell transfusion without evidence of haemolysis
- A significant intervention, for example:
 - Endoscopy to treat the bleeding
 - Interventional radiography to treat the bleeding
 - Transfer to the operating theatre/room for treatment of bleeding

(Please also see organ-specific definitions)

Grade 2

Any bleeding that does not fulfil the requirements for grade 3 bleeding (general or organ-specific) BUT requires an intervention or treatment:

- Examples of Interventions
 - Nasal Packing
 - Bladder irrigation
- Examples of treatments
 - Platelet transfusion given to treat active bleeding and NOT given only because the platelet count is below the prophylactic platelet transfusion trigger
 - Medications prescribed to treat bleeding

(Please also see organ-specific definitions)

Grade 1

Any bleeding that does not fulfil the requirements for grade 2 bleeding (general or organ-specific). For examples of grade 1 bleeding please see the organ-specific definitions.

Organ-specific definitions of WHO Grades

	Grade 1	Grade 2	Grade 3	Grade 4

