Soft-tissue and musculoskeletal	Asymptomatic spontaneous soft-tissue haematoma less than 10cm in diameter. Traumatic haematoma of any size Traumatic joint bleeding (confirmed by aspiration, imaging study or other accepted technique)	Asymptomatic spontaneous soft-tissue haematoma greater than 10cm in diameter. Symptomatic soft-tissue haematoma (e.g. causing pain or discomfort). Spontaneous joint bleeding (confirmed by aspiration, imaging study or other accepted technique)		Any bleeding that causes compartment syndrome.
Gastrointestinal	Faecal occult blood Rectorrhagia- visible red blood on tissue paper/not mixed with stool	Melaena Hematochezia – visible red blood mixed in stool, not requiring a transfusion Haematemesis – Grossly visible blood in emesis (vomit) or in nasogastric drainage tube (not related or secondary to swallowed blood)		

Genitourinary	Abnormal vaginal bleeding (Unexpected bleeding out of normal cycle OR Bleeding heavier than normal OR Breakthrough bleeding (patient on hormonal therapy to prevent bleeding)) with spotting Microscopic haematuria/dipstick positive haematuria	Abnormal vaginal bleeding (Unexpected bleeding out of normal cycle OR Bleeding heavier than normal OR Breakthrough bleeding (patient on hormonal therapy to prevent bleeding)) more than spotting Gross/visible haematuria	Any bleeding that causes: increase ≥ 1.5 X reference serum creatinine \neq or Serum creatinine rises by $\geq 26\mu\text{mol/L}$ (0.3mg/dl) within 48 hours or Urine output <0.5 mL/kg/hr for > 6 consecutive hrs	Any bleeding that causes: increase ≥ 3 X reference serum creatinine \neq or Serum creatinine rises by $\geq 354\mu\text{mol/L}$ (4.0 mg/dl) or Commenced on renal replacement therapy or Urine output <0.3 mL/kg/hr for > 24 hrs or Anuria for at least 12 hrs
Pulmonary		Haemoptysis – Visible blood Blood in broncho-pulmonary lavage, or blood tinged sputum (excluding those with nose or oropharyngeal bleeding or mucositis).	Any bleeding requiring supplemental oxygen to maintain oxygen saturation above 93%.	Any bleeding requiring respiratory support (includes non-invasive (CPAP, BiPAP), or invasive ventilation)
Body cavity		Visible blood in body cavity fluid (e.g. red cells apparent in fluid aspirate) short of criteria for Grade 3 or 4	Grossly visible blood in body cavity fluids AND organ dysfunction with symptoms, AND/OR need to intervene (e.g. to aspirate).	

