## 2. Outcome Measures

### 2.1 Primary outcome measures

Estimated proportion of participants who died or had bleeding of WHO grade 2 or above during the first 30 days of the trial **from the first day of administration of the study intervention.**

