### 4.7 Sensitivity analyses

- The key demographics and clinical condition of participants at consent will be described for each arm of the trial, comparing all randomised participants with the mITT population to ensure that excluded participants are similar across the arms.
- Per-protocol analysis of the primary outcome. This analysis will exclude all participants who did not adhere to a set of minimum protocol-adherence criteria during the first 30 days of the trial. Participants who were randomised in error will be excluded from this analysis. The per-protocol analysis will be performed using the same method as for the mITT analysis. Protocol-adherence will be summarised by treatment arm. In addition, since the per-protocol analysis may lead to an over-estimation of the difference in the proportion experiencing the primary outcome in each treatment arm, which may be explained by differing levels of protocol-adherence in each treatment arm, an instrumental variable analysis will be performed. The randomisation arm will be used as the instrument. The instrumental variable estimate will be calculated as the mITT estimate of the difference in the proportion experiencing the primary outcome in each treatment arm / proportion adhering to the minimum compliance criteria in the active treatment arm. The standard error of the instrumental variable estimate will be calculated using two-stage least squares.
- Some participants may withdraw or be lost to follow up during the conduct of the trial. In addition, some participants who are followed up for the full 30 days may be missing some bleeding assessments. In these cases, it is impossible to know whether such participants would be either less or more likely to experience bleeding if they had complete bleeding assessments for the full 30-day follow up period. Sensitivity of the primary outcome to incomplete follow up and missing bleeding assessments will be assessed by re-calculating the primary outcome, by arm, for all participants included in the mITT analysis, after imputing all missing bleeding assessments up to study day 30.

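### The per-protocol criteria run past the first primary event, so treating a bleed, or dosing after one, can remove a participant together with the event; the direction of the resulting bias is unknown

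*SAP*

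**What the plan says.** SAP 4.2.1 defines a per-protocol analysis of the primary outcome. It excludes people randomised in error and "all participants who did not adhere to a set of minimum protocol-adherence criteria during the first 30 days of the trial". There are four criteria, and Protocol 11.4 has the same four. Two matter here:

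- the participant received only the prescribed trial treatment and "did not receive open label tranexamic acid, other antifibrinolytic agent or procoagulant drug";
- "The participant did not receive trial treatment after the point at which discontinuation of trial treatment should have occurred".

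Neither document says that the criteria stop applying once the participant has had a primary event. SAP 4.2.1 does say that missed doses, a participant's choice to stop early, and withdrawal after starting treatment do not exclude.

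The primary outcome covers the same 30 days: "Estimated proportion of participants who died or had bleeding of WHO grade 2 or above during the first 30 days of the trial". Protocol 20.2 defines grade 2 as "Any bleeding that does not fulfil the requirements for grade 3 bleeding (general or organ-specific) BUT requires an intervention or treatment" and gives "Medications prescribed to treat bleeding" as an example of such treatment. In the genitourinary row, "Gross/visible haematuria" is grade 2. Protocol 6.2.6 lists visible haematuria, and receipt of open-label TXA or a similar drug, among the points at which trial treatment stops for good.

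SAP 4.7 adds an instrumental-variable estimate, "since the per-protocol analysis may lead to an over-estimation of the difference". It divides the mITT risk difference by the proportion of the active arm that met the same criteria.

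**The concern.** For a time-to-first-event outcome, a participant's contribution is complete at the first event. What happens afterwards cannot have affected whether or when that event occurred. Here, what happens afterwards decides whether the participant is analysed at all, and one of the deciding acts, giving a drug for the bleed, is a consequence of the event. That is selection on the outcome, and comparing participants as randomised does not protect against it.

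The rule is also wider than non-adherence in the ordinary sense. Protocol 6.4.4 bars these drugs only while trial medication is being taken. A participant who had correctly finished trial treatment and then received open-label TXA for a bleed before day 30 would not have breached that section, yet would leave the per-protocol set.

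At stake is how a disagreement between the per-protocol and mITT results is read. The SAP prepares the reader for only one direction of disagreement.

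**Working it through.** **Inputs.** Risks of 43% (placebo) and 32% (TXA), two-sided 0.05, 80% power and a required 586 participants come from Protocol 11.3.2 and SAP 1.5.2. The share of primary events removed in an arm, *f*, is an assumption, because neither document gives a rate of open-label use or of dosing after haematuria.

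**The plan's own figures.** The plan gives none for the per-protocol exclusion. The planning risks behave as stated: HR = ln(1 − 0.32)/ln(1 − 0.43) = 0.686. The log-rank events formula gives 222 events, and 222/0.375 = 592 participants, close to the stated 586.

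**Formula.** If a share *f* of those with an event is removed and no one else is, the per-protocol risk is

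p′ = p(1 − f)/(1 − pf).

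The odds become p(1 − f)/(1 − p). The odds ratio is therefore multiplied by (1 − f_TXA)/(1 − f_placebo), and equal removal leaves it at 0.624. The HRs below are ln(1 − p′_TXA)/ln(1 − p′_placebo), assuming proportional hazards.

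Example, 20% of placebo and 10% of TXA events removed:

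- placebo: 0.43 × 0.80/(1 − 0.086) = 0.344/0.914 = 37.6%
- TXA: 0.32 × 0.90/(1 − 0.032) = 0.288/0.968 = 29.8%
- difference 7.9 points, HR 0.75

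| True risks | f placebo / TXA | Per-protocol risks | Difference (points) | HR |
|---|---|---|---|---|
| 43% / 32% | 0 / 0 | 43.0% / 32.0% | 11.0 | 0.69 |
| 43% / 32% | 5% / 5% | 41.8% / 30.9% | 10.9 | 0.68 |
| 43% / 32% | 25% / 25% | 36.1% / 26.1% | 10.0 | 0.67 |
| 43% / 32% | 20% / 10% | 37.6% / 29.8% | 7.9 | 0.75 |
| 43% / 32% | 10% / 20% | 40.4% / 27.4% | 13.1 | 0.62 |
| 43% / 43% | 20% / 10% | 37.6% / 40.4% | −2.8 | 1.10 |
| 43% / 43% | 10% / 20% | 40.4% / 37.6% | +2.8 | 0.91 |

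Equal removal shrinks the risk difference slightly and moves the HR slightly away from 1. Unequal removal moves both in whichever direction the imbalance runs, and can create a difference where there is none.

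**Events lost.** With 586/2 = 293 per arm and f = 20%: 293 × 0.43 × 0.20 = 25 placebo events and 293 × 0.32 × 0.20 = 19 TXA events.

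**Instrumental-variable estimate.** The numerator is the mITT difference, so no event is lost there. The denominator falls. If this were the only source of non-adherence, the estimate would be 11.0/(1 − 0.32 × 0.20) = 11.0/0.936 = 11.75 points when 20% of active-arm events are removed.

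**The case against.** A reader might infer that the rule strips out events and leaves every non-event in place. The documents do not support that. Most discontinuation points in Protocol 6.2.6 are not bleeds: day 30, platelet recovery, starting an anticoagulant, thrombosis, anuria, veno-occlusive disease. A participant who never bled and was dosed after platelet recovery is excluded as a non-event, as is one given a procoagulant for another reason. Late starts and wrong doses can also remove non-events. Bleeds not treated with these drugs, and deaths, stay in unless another criterion applies. The table models one mechanism, so it does not show that the whole per-protocol set understates risk.

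A reader might also infer bias towards no effect, on the view that placebo bleeds are worse and attract more open-label treatment. Nothing in the documents says which arm would have more crossover, and the reverse imbalance gives the over-estimation that SAP 4.7 already names.

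Three further points stand in part. This is a sensitivity analysis, and the mITT analysis keeps all these participants. The SAP tabulates adherence, reasons for discontinuation and medication that lowers bleeding risk by arm, so a large imbalance would be visible; but seeing it does not undo the exclusion. Finally, grade is assigned by a central algorithm (Protocol 8.2.2) whose specification is not in the documents, so the link from drug treatment to grade 2 rests on the definition in Protocol 20.2.

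**Conclusion.** The point holds in a limited form. Read together, SAP 4.2.1, Protocol 11.4 and Protocol 20.2 remove some primary events because of what was done after them. The per-protocol set is partly selected on the outcome, and the instrumental-variable denominator inherits the fault.

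The size depends on an unknown removal rate. If the rate is similar in both arms the contrast hardly changes: at 25% in each, 10.0 points and HR 0.67. If the rates differ by a factor of two, as in the 20%/10% and 10%/20% cases, the difference ranges from 7.9 to 13.1 points against a true 11.0. The direction cannot be determined from the documents, so a caveat naming over-estimation alone is incomplete. The primary mITT result and the sample size are not touched. The change is worth making before results are seen, but it does not threaten the trial's main conclusion.

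**What to change.** In SAP 4.2.1 and 4.7 and in Protocol 11.4:

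1. State that open-label antifibrinolytic or procoagulant use, or any other deviation, on or after the date of the first primary event does not make a participant non-adherent, either for the per-protocol set or for the instrumental-variable denominator. Working by date avoids having to attribute each drug to a particular bleed.
2. Deal with the side effect. Participants with an event now have a shorter adherence window than those without, so a later deviation can exclude only someone still event-free at that time. Either censor participants who deviate after Day 1 but before any event at the date of deviation, instead of excluding them, or keep the exclusion and state this limitation.
3. Amend the SAP 4.7 caveat to say that per-protocol bias may go in either direction.

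The cost is wording in both documents and a little programming to date deviations relative to events. Protocol 6.2.6 requires use of these agents to be recorded; that the dates are captured should be confirmed on the forms. Censoring at deviation may itself be informative, and the report should say so. No clinical rule changes.
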